#### **4.3. Randomization Criteria**

A list of allowed and disallowed concomitant pain medication is provided in sections 5.3.7 and 5.3.8. If patients is on any of the disallowed pain medications, this medication will be discontinued during the washout phase with an appropriate taper schedule based on the clinician judgment. Subjects must meet the following criteria after the washout period to be randomized for single-blind pregabalin treatment phase:

1. Subjects must have worsening in neuropathic pain from baseline to the end of washout phase.
2. Subjects must have an average pain score  $\geq 8$  in the final week of washout phase.

Subjects must meet the following criteria after the single-blind pregabalin treatment phase to be randomized for withdrawal phase:

1. Subjects must have response to treatment defined as at least one point decrease in pain intensity score at the end of the single-blind pregabalin treatment phase.

#### **4.4. Life Style Guidelines**

Subjects should not initiate or alter an exercise regimen during the study, as this could influence efficacy results based on the pain scale scores.

Subjects should not modify stable medication regimens, and should not have surgery or interventional medical procedures for the duration of the study.

Female patients at child bearing age must be informed that pregabalin is a category C medication for pregnancy which means that a risk cannot be ruled out and therefore use of an effective birth control method is recommended.

### **5. STUDY TREATMENTS**

During the screening phase, the medication history of the subjects who are eligible for the study based on meeting the inclusion and exclusion criteria will be reviewed. The current pain medications of the subjects will be categorized into allowed and disallowed medications (see sections 5.3.7 and 5.3.8 for a complete list of these medications). If patient is on any of the

disallowed neuropathic pain medication such as gabapentin, these medications will be discontinued during the washout phase. A written instruction will be provided to the patient on how to discontinue the medication during the washout phase. Patient will complete a daily pain diary during this phase. Patient can continue to take the allowed pain medications but no change in dose or frequency is permitted. At the end of the washout period which is at least 14 days and might be longer based on the type of medication being discontinued, patient will be evaluated for eligibility for the study again based on randomization criteria mentioned in section 4.3.

All patients entering the study will be treated with single-blind pregabalin at doses of 150-600 mg/day for 8 weeks. The first 4 weeks of the single-blind phase comprise the dose optimization phase, and the next 4 weeks the single blind maintenance phase.

During the initial week of the single-blind pregabalin treatment phase, all patients will be treated with pregabalin 150 mg/day, and dose is to be increased based on response and tolerability until the end of Week 4. If the patient is unable to tolerate the higher dose, the dose should be reduced by one dose level per investigator discretion. This dose reduction may occur outside of the scheduled visit. Patients unable to tolerate a dose of 150 mg/day pregabalin during the Single-Blind phase will discontinue from the study (no taper necessary). After the end of the 4th week of the Single-Blind phase, no further dose escalation is permitted. During the next 4 weeks of the Single-Blind phase, fixed dose pregabalin treatment at the optimized dose within the range of 150 to 600 mg/day administered BID will be provided. One additional dose reduction may occur if needed during the last 4 weeks of the single blind period. Patients unable to tolerate the fixed dose of study medication will be discontinued from the study.

Patients meeting all eligibility criteria for withdrawal phase will be randomized in a 1:1 fashion to continue the fixed dose of pregabalin treatment as they were taking in the Single-Blind phase or placebo. Patients will continue in the withdrawal portion of the study for 4 weeks.

Patients who discontinue from the study during or at the end of the single-blind pregabalin treatment phase will complete a taper. Patients who had been receiving pregabalin 450 or 600 mg/day will receive pregabalin 300 mg/day for 4 days and 150 for 3 days. Patients receiving pregabalin 150 or 300 mg/day will receive 150 mg/day for 4 days and 50 mg for 3 days. Patients who have not taken study medication for the past 24 hours or more are not required to receive the taper medication.

At the end of the single-blind pregabalin treatment phase, patients will be randomized to receive either pregabalin at the optimized dose (150-600 mg/day pregabalin), as determined during the treatment phase, or matching placebo. No further dose adjustments will be allowed.

#### **Patients randomized to pregabalin will continue at the optimized pregabalin dose**

**Patients randomized to placebo** who were receiving pregabalin 450-600 mg/day will be tapered to placebo to mask any changes in adverse events. The taper will consist of pregabalin 300 mg/day for 4 days and 150 mg/day for 3 days. Subsequently these patients will receive placebo. Placebo treatment will continue until end of withdrawal period.

**Patients randomized to placebo** who were receiving 150-300 mg/day pregabalin will receive 150 mg/day for 4 days and 50 mg/day for 3 days during the first week of the withdrawal phase, then which will continue through the end of withdrawal phase.

At any time during the study (single-blind pregabalin treatment or withdrawal), if the patient cannot tolerate a dose of 150 mg/day pregabalin (or matching placebo in withdrawal phase) the patient will discontinue from the study, with no taper necessary. Patients experiencing inadequate pain relief should be assessed to determine whether the pain level is tolerable to complete the study or will need to be withdrawn due to lack of efficacy. Subjects requiring dosing adjustment during the withdrawal phase will be discontinued.

### **5.1. Allocation to Treatment**

Subjects will be assigned a single subject identification number (SSID). This number will be retained throughout the study. A separate randomization number will be assigned by the experimental pharmacy at randomization and will be recorded on the case report form.

Following the treatment phase, qualified patients will be randomized in a 1:1 ratio to receive either pregabalin at the optimized dose or placebo.

### **5.2. Breaking the Blind**

The study drug and placebo will be identical in appearance in order to preserve the study blinding. The investigator will be aware of the subject's treatment during the study but will not share this information with the subject. Blinding should only be broken for serious, unexpected, and related adverse events, and only for the subject in question, or when required by local regulatory authorities. Subjects whose randomization codes are broken in this way will be withdrawn from the study. The investigator must record the reason for breaking the blind in the subject's source documents.

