### 3. STUDY DESIGN

This enriched enrollment randomized withdrawal study comprises 4 phases: a screening and selection phase, a 2-4 weeks washout period from previous pain medication for enriched enrollment, an 8 week single-blind pregabalin treatment phase; and a 4 week randomized withdrawal phase. Patients who show any increase in their pain intensity score during the washout phase will be eligible for the single blind pregabalin treatment phase. Patients who respond to pregabalin, with at least 1 point improvement in neuropathic pain from baseline at the end of the single-blind pregabalin treatment phase and meeting all other study requirements are considered eligible for participation in the withdrawal phase. These eligible patients are randomly assigned (1:1) to continue pregabalin or to be switched to placebo for a comparison of pregabalin efficacy and safety. Patients who have a worsening of average pain relative to the last week of the single blind pregabalin treatment period by more than one point and average pain level  $\geq 4$  will be considered to have a loss of therapeutic response (LTR).

\*Low creatinine clearance patients: 150-300 mg/day

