### **5.3.3. Administration**

Throughout the study, patients will be blinded to the treatment they are receiving. After the washout period, patients who meet eligibility criteria will be randomized to receive pregabalin or matching placebo for the remainder of the study phase. Once a subject has been randomized, the subject will be blinded to the treatment assignment.

During the single-blind pregabalin treatment and withdrawal phase patients will take 1 capsule twice daily. The study medication will be administrated orally, BID, with or without food. Sufficient study medication will be provided to cover visit windows.

Subjects should be instructed on use of the study medication. When patients are dispensed multiple bottles of study medication, instruct the patient carefully regarding which bottle to use

and to take study medication from only one bottle at a time. Dose adjustments may be made by telephone.

Subjects should return medication bottles and any unused tablet(s) in each bottle to the site. Any dosing errors must be fully documented in source documentation and (if applicable) in the case report form. Dosing errors that may impact subject safety will be discussed by the investigator and sponsor.

Medication errors are reportable irrespective of the presence of an associated AE/SAE, including:

Medication errors involving patient exposure to the product.

Potential medication errors or uses outside of what is foreseen in the protocol that do or do not involve the participating subject.

Whether or not the medication error is accompanied by an AE, as determined by the investigator, the medication error and, if applicable, any associated adverse event(s) is captured on an adverse event (AE) CRF page (refer to Adverse Event Reporting section for further details).

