### **5.3.7. Allowed Medications**

The following medications are permitted as described below. Medications listed must be taken for the indications specified, must be stable for the periods indicated prior to the first visit, and may not exceed the doses specified for subjects to be eligible for study participation. Subjects who do not meet these criteria are excluded from participation in the study.

Class of Medication	Examples (not a comprehensive list)	Minimum Period on Medication Prior to V1
----------------------------	---	---

Analgesics	Acetaminophen	Maximum dose of acetaminophen or any acetaminophen-containing products should not exceed 3 grams/day
	NSAIDS, COX-2 inhibitors	Patients using NSAIDS at the start of the trial for conditions other than neuropathic pain may continue but should not change the pattern of use during the trial. NSAIDs may be initiated for acute conditions during the trial unrelated to neuropathic pain if clearly clinically necessary for the care of the patient.
	Aspirin	For myocardial infarction and stroke prophylaxis
Antidepressants	Antidepressants other than TCAs and SNRIs	Stable for one month prior to V1; therapy may not be initiated during the study. A maximum of one antidepressant may be used.
Benzodiazepines	Lorazepam	Subjects must be on a stable regimen within the last month (only bedtime dose; prescription for sleep only). Therapy may not be initiated during the Single-Blind or Double-Blind Phase. Long Life benzodiazepines(Diazepam) are not allowed.

GABA A partial agonists	Zolpidem Eszopiclone	Subjects must be on a stable regimen within the last month. Therapy may not be initiated during the Single-Blind or Double-Blind Phase.
Antihistamines		For allergy nonsedating antihistamines should be

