#### **6.2.5. Visit 6 (Day 56) – Clinic Visit**

Review adverse events, the daily pain and sleep diary, the dosing diary, concomitant medications, and non-drug treatments. Remind the patient to continue completing diaries until the next scheduled visit.

The C-SSRS will be completed by the patient and reviewed to determine if a risk assessment is required.

Perform the following assessments: NPSI, SFN-SIQ, BPI-SF, and EQ-5D

Determine from the IVRS system whether the patient meets the pain improvement criterion to be randomized into the withdrawal Phase of the study. If the patient meets response criteria, the patient continues in the study and is to be randomized at this visit. Blinding is to be maintained.

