## **9.2. Safety Analysis**

Safety data will be presented separately for both single-blind and double-blind phases of the study. Safety data will be tabulated and listed according to Pfizer's standard reporting algorithms.

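### Section 5.2 makes the investigator aware of treatment with no phase limit, while 5.3.7 and 9.2 call the randomised withdrawal phase double-blind; the protocol must state who is blinded from Visit 6

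*Combined protocol and SAP*

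**What the plan says.** Section 5.2, the section on blinding, says of the investigator: "The investigator will be aware of the subject's treatment during the study but will not share this information with the subject". It then restricts when the blind may be broken, requires the investigator to record the reason, and adds: "Subjects whose randomization codes are broken in this way will be withdrawn from the study".

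Section 5.3.3 speaks only of the patient: "Throughout the study, patients will be blinded to the treatment they are receiving". It also says: "After the washout period, patients who meet eligibility criteria will be randomized to receive pregabalin or matching placebo". That timing disagrees with Sections 3, 5 and 5.1, which put randomisation after the single-blind treatment phase.

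Two other places use a different label. In 5.3.7, the table rows for benzodiazepines and for GABA-A partial agonists say: "Therapy may not be initiated during the Single-Blind or Double-Blind Phase". Section 9.2 says: "Safety data will be presented separately for both single-blind and double-blind phases of the study".

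Section 3 describes the treatment part of the study as "an 8 week single-blind pregabalin treatment phase; and a 4 week randomized withdrawal phase" and gives the second of these no blinding label. At Visit 6 (6.2.5) the responding patient "is to be randomized at this visit. Blinding is to be maintained", without saying for whom.

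**The concern.** The withdrawal phase is the only randomised comparison in the trial. A sentence that makes the investigator aware of treatment throughout the study cannot stand beside a label that calls this phase double-blind in the usual sense of the term, and the protocol defines no other sense. Two sites could read the same protocol and act differently: one would follow 5.2 and learn the arm, the other would follow the label and not. The report would then describe the phase as double-blind in either case.

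If 5.2 is followed, two investigator-dependent steps take place with knowledge of the arm: deciding whether a patient with inadequate relief stays in the study, and rating the causality of adverse events.

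**Working it through.** No figure in the plan bears on this point, so the check is a comparison of the text.

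1. **Which phase is the double-blind one?** Section 3 and the schedule in Appendix 1 contain two phases on study drug: 8 weeks of single-blind pregabalin and 4 weeks of randomised withdrawal. Since 5.3.7 and 9.2 set a double-blind phase beside the single-blind one, it can only be the withdrawal phase.

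2. **What does 5.2 say about that phase?** Its period is the study as a whole. Nothing in the sentence, or elsewhere in 5.2, confines it to the first 8 weeks.

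3. **Does any other section blind the investigator from Visit 6?** None does so expressly.
   - 5.3.3 names patients and subjects only, and its misplaced timing of randomisation makes it uncertain that its post-randomisation sentence describes Visit 6 at all.
   - 5.1 has the experimental pharmacy assign a randomisation number, which goes on the case report form. It does not say whether the investigator learns the arm.
   - 6.2.1 to 6.2.4 ask for blinding to be kept with the patient, but these visits belong to the single-blind phase.
   - 6.2.5 (Visit 6) asks for blinding to be kept and drops the reference to the patient.
   - 6.2.5.2 keeps the fact of randomisation from the patient and mentions no one else.

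4. **Is 5.2 consistent with itself?** Not comfortably. A restricted code-break, a recorded reason and withdrawal of the subject afterwards serve little purpose if the investigator already knows the arm. They could still be read as rules on disclosure to the subject, so they do not decide the matter.

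5. **Where could awareness act?**
   - *Primary endpoint, directly:* limited. Under 7.2.1 and 7.2.1.1 the patient scores pain in a diary, and the patient is blinded on every reading.
   - *Primary endpoint, through missing data:* Section 5 has patients with inadequate relief assessed to see whether they can complete or must be withdrawn for lack of efficacy. It names no assessor. Such withdrawals pass into the BOCF/mBOCF handling in 9.1.1.
   - *Safety:* under 8.8 the investigator rates causality for every adverse event. Under 8.7 the investigator also rates severity, if the form requires it.
   - *Records:* Section 5 gives only the placebo arm a taper in the first week of withdrawal, and 5.3.2 has the investigator maintain dispensing records. Those records could show the arm even after 5.2 is reworded.

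6. **Can the effect be sized?** No. Nothing links investigator awareness to a number of withdrawals or to a shift in ratings, and 9.1.1 does not say which baseline is carried forward or define mBOCF, so even the direction is open. For scale only: with the 20 patients per group in 9.1, one withdrawal is 1/20 = 5% of an arm. That is not an estimate of bias.

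**The case against.** The strongest reply is that the 5.2 sentence is run-in text left without a phase limit, and that the rest of the protocol points to a wider blind from Visit 6. The visit instructions refer to the patient through the single-blind phase and drop that qualifier at randomisation. The pharmacy assigns the randomisation number, capsules and bottles are identical (5.3.1), bottles are not subject-specific and the pharmacy dispenses them (5.3.2), and a code-break rule exists. This has force and may well be the intent. It remains inference: no section says it, and the section a site would consult on blinding says the opposite.

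A second reply is that little is at stake. The primary score is self-rated, loss of therapeutic response in Section 3 is defined by pain-score thresholds rather than opinion, and 9.2 tabulates and lists safety data without testing. This stands in large part and limits the weight of the point. It does not cover withdrawal for lack of efficacy in Section 5, which rests on whether pain is tolerable and not on those thresholds, or the causality ratings.

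A third is that the conflict could be removed from the other side, by correcting the label. Double-blind describes this study only in a medication table and one safety sentence. That is a legitimate resolution if it is what the sponsor intends.

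A reader might infer from 5.2 that investigators will in fact know every allocation. The documents do not support that: no procedure passes the arm to the investigator, and the inference rests on one sentence that conflicts with its own section.

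**Conclusion.** The contradiction is real and concerns the only randomised phase. The protocol states a rule (investigator aware, no phase limit) that conflicts with a property it claims elsewhere (double-blind), and no section resolves it. It should be corrected before sites act on the text and before the phase is reported as double-blind.

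The weight is moderate. The patient-rated diary limits the effect on the primary endpoint. The exposed parts are withdrawal for lack of efficacy feeding BOCF/mBOCF, and adverse event causality, by an amount and in a direction that the documents do not give. A reader might go further and conclude that the primary result is biased; nothing in the documents shows that.

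The conclusion assumes that double-blind has its usual meaning, covering patient and investigator, and that the investigator or site staff carry out the lack-of-efficacy assessment, since Section 5 names no one.

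**What to change.** - In 5.2, limit the investigator's awareness of treatment to the 8-week single-blind phase.
- In 5.2 and 5.3.3, state that from randomisation at Visit 6 the subject, the investigator and site staff are blinded and that only the experimental pharmacy holds the allocation. Keep the existing code-break rule, and add that the pharmacy releases the code for the one subject concerned.
- Have the pharmacy keep the dispensing records for the withdrawal phase, including the placebo-arm taper week, so that they do not reveal the arm. Adjust the investigator's record duty in 5.3.2 to match.
- Reconcile 5.2, 5.3.3 (including its timing of randomisation), 5.3.7, 6.2.5 and 9.2, so that each says the same about who is blinded in which phase.
- If the sponsor intends the investigator to remain aware, call the phase single-blind in 5.3.7, in 9.2 and in every report.

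The cost is small: protocol wording and a change in who holds certain records. The pharmacy already assigns the randomisation numbers and dispenses the medication, and the capsules and bottles are already identical. No change to sample size, visits or analysis model is needed.

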### **5.3. Drug Supplies**

#### **5.3.1. Formulation and Packaging**

Study medication will be supplied as blinded capsules of pregabalin and matching placebo. The pregabalin capsules are composed of pregabalin, lactose monohydrate, cornstarch, and talc encapsulated in opaque hard gelatin capsule shells composed of gelatin and titanium dioxide. The placebo capsules will contain lactose monohydrate, microcrystalline cellulose, sucrose octaacetate, and magnesium stearate.

STUDY DRUG	
Generic name:	Pregabalin
Trade name:	Lyrica
Dosage form:	Capsules
Strength:	75 mg, 150 mg, 225 mg, 300 mg
Manufacturer:	Pfizer PPD, Freiburg, Germany
Supplier:	Pfizer Global Research Development
Ingredients:	Active: Pregabalin Inactive: Lactose monohydrate, corn starch, talc, gelatin, titanium dioxide, black iron oxide
Description:	Grey/Grey #0 capsules
PLACEBO	
Dosage form:	Capsules
Manufacturer:	Pfizer PPD, Freiburg, Germany
Supplier:	Pfizer Global Research Development
Ingredients:	Lactose monohydrate, microcrystalline cellulose, sucrose octaacetate, magnesium stearate, gelatin, titanium dioxide, black iron oxide
Description:	Grey/Grey #0 capsules identical in appearance to Pregabalin

The active trial medication and the placebo will be of identical appearance, and packaged in identical bottles.

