### APPENDIX 3. Study Medication Taper Schedule

Pregabalin Dose	Taper Day 1 (mg/day)	Taper Day 2 (mg/day)	Taper Day 3 (mg/day)	Taper Day 4 (mg/day)	Taper Day 5 (mg/day)	Taper Day 6 (mg/day)	Taper Day 7 (mg/day)
150 mg	150	150	150	150	50	50	50
300 mg	150	150	150	150	50	50	50
450 mg	300	300	300	300	150	150	150
600 mg	300	300	300	300	150	150	150

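### The 50 mg/day taper step for patients on 150 or 300 mg/day cannot be made from the capsule strengths that the protocol lists

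*Combined protocol and SAP*

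**What the plan says.** **Supply.** Section 5.3.1 gives the strengths as "75 mg, 150 mg, 225 mg, 300 mg". The product is a hard capsule, "encapsulated in opaque hard gelatin capsule shells composed of gelatin and titanium dioxide". No other dosage form is described.

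**Administration.** Section 5.3.3 states: "During the single-blind pregabalin treatment and withdrawal phase patients will take 1 capsule twice daily". Patients given several bottles are told "to take study medication from only one bottle at a time".

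**Taper at the switch to placebo.** Under Section 5, placebo-arm patients who had been on 150-300 mg/day "will receive 150 mg/day for 4 days and 50 mg/day for 3 days during the first week of the withdrawal phase". For those who had been on 450-600 mg/day, "The taper will consist of pregabalin 300 mg/day for 4 days and 150 mg/day for 3 days". The protocol gives a masking purpose for this higher-dose taper only.

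**Taper at discontinuation.** Section 5 also says: "Patients receiving pregabalin 150 or 300 mg/day will receive 150 mg/day for 4 days and 50 mg for 3 days". The 150 mg and 300 mg rows of Appendix 3, "Study Medication Taper Schedule", show 50 mg/day on each of days 5, 6 and 7.

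**Taper supply.** Section 6.2.5.1 (discontinuation) and Section 6.2.6 (Visit 7) mention a taper bottle but not what it contains. Section 6.2.5.2, which covers dispensing at randomisation, describes no taper supply.

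**The concern.** One part of the protocol sets a dose that the supply described in another part cannot produce. No 25 mg or 50 mg strength appears anywhere in the document, yet the 50 mg step appears in three places: two paragraphs of Section 5, and Appendix 3. A single slip of the pen is therefore unlikely.

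The switch to placebo is where it matters most, because that taper falls in the first week of the randomised comparison. Section 5.3.2 tells the pharmacy to dispense as the protocol sets out, and for this step it cannot. Someone must then choose a substitute, possibly a different one for each patient. Placebo-arm exposure in that week could then vary in a way the protocol does not define, and a visibly different regimen could weaken masking. Section 5.2 says the investigator knows the treatment, so blinding rests on the patient, who also rates the pain.

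Patients on 150 mg/day are the most exposed. Their taper days 1-4 are at the dose they were already taking, so the 50 mg step is their only step-down.

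**Working it through.** **Inputs**
- Strengths: 75, 150, 225 and 300 mg (Section 5.3.1).
- Rule: one capsule twice daily (Section 5.3.3), from a single bottle where several are dispensed.
- Doses to be made: 150, 300, 450 and 600 mg/day (maintenance, Section 5 and Appendix 3); 300 then 150 mg/day (taper from 450 or 600); 150 then 50 mg/day (taper from 150 or 300).

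**Step 1. Does the strength list reproduce the other doses?** With two identical capsules a day, the dose is 2 × strength:

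| Strength (mg) | Daily dose (mg) |
|---|---|
| 75 | 150 |
| 150 | 300 |
| 225 | 450 |
| 300 | 600 |

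These are exactly the four maintenance doses. Both steps of the taper from 450 or 600 mg/day (300, then 150) can be made, as can days 1-4 (150 mg/day) of the lower taper.

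**Step 2. Can 50 mg/day be made?** Three readings, from strict to loose:

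| Reading | Obtainable daily doses (mg) | Lowest active dose (mg) | 50 mg? |
|---|---|---|---|
| Two identical capsules from one bottle | 150, 300, 450, 600 | 150 | No |
| Any two capsules, placebo allowed as one or both | 0, 75, 150, 225, 300, 375, 450, 525, 600 | 75 | No |
| Any number of whole capsules | Multiples of 75 only | 75 | No (50/75 = 0.67, not a whole number) |

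The shortfall therefore does not depend on the one-bottle instruction. The lowest active dose is 150/50 = 3 times the stated step on the strict reading, and 75/50 = 1.5 times with a placebo partner.

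**Step 3. Could the three days average 50 mg?** The three-day total is 3 × 50 = 150 mg, which equals two 75 mg capsules (75, 75, 0). That averages 50 mg/day, but Appendix 3 puts 50 mg on each of the three days.

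**Step 4. Who loses what at the switch to placebo?**

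| Dose before switch (mg/day) | Days 1-4 | Days 5-7 | Without the 50 mg step |
|---|---|---|---|
| 150 | 150 (no reduction) | 50 (not deliverable) | No step-down remains |
| 300 | 150 (deliverable) | 50 (not deliverable) | One step-down remains |
| 450 or 600 | 300 (deliverable) | 150 (deliverable) | Not affected |

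**Step 5. Duration.** Three days out of 4 × 7 = 28 days of the withdrawal phase.

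**The case against.** **The strength list may cover treatment doses only.** Since its four strengths doubled give exactly the maintenance doses, the taper bottles might hold something else. This stands in part: an unlisted strength may exist in practice. But Section 5.3.1 would then be incomplete, and the taper bottles are mentioned only for discontinuation and Visit 7, not for the switch at randomisation.

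**The abrupt drop is one that the protocol already accepts.** A reader might infer a safety problem from patients going from 150 mg/day straight to placebo. The documents do not support that as a separate claim. The taper from 450 or 600 mg/day also ends at 150 mg/day and then placebo, and patients who cannot tolerate 150 mg/day stop without a taper. This objection stands.

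**Unblinding.** A reader might infer that the missing step reveals the switch. The masking purpose is stated only for the higher-dose taper. Withdrawal confined to the placebo arm is inherent in this design and would remain if 50 mg could be supplied. Section 6.2.5.2 also says patients should not be told that randomisation or a treatment change may happen at that visit. What remains is a risk from improvised dispensing, not demonstrated unblinding.

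**Bias in the primary result.** The step falls on days 5-7, well before the last treatment week, where Section 9.1.1 handles missing data. Early dropout could carry through under BOCF, but nothing in the documents allows that to be sized. A taper after Visit 7 follows the comparison and cannot bias it.

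**Scope.** It would be wrong to say that everyone who discontinues from 150 or 300 mg/day is affected. Section 5 exempts patients who have been off drug for 24 hours or more and those intolerant of 150 mg/day. Appendix 2 moves patients who tolerate treatment up to 300 mg/day at Visit 3 and 450 mg/day at Visit 4, so those still on 150 or 300 mg/day are the ones held back or reduced. Their number is unknown.

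**Conclusion.** The point holds as an internal inconsistency of low severity. The 50 mg/day step on taper days 5-7 cannot be made from any whole-capsule combination of the listed strengths; every other stated dose can. It concerns placebo-arm patients who were on 150 or 300 mg/day, for 3 of 28 randomised days, and non-exempt patients tapering from those doses at discontinuation or after Visit 7. Patients on 150 mg/day lose their only step-down; those on 300 mg/day keep one.

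This assumes that the strength list is complete and that capsules are taken whole, since no splitting or other form is described. If an unlisted taper strength is in fact supplied, the error lies in the supply section and not in the schedule, but the two still need to agree.

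The consequence that can be supported is improvised dispensing in the first randomised week, with a risk of inconsistent placebo-arm exposure and masking. The number of patients affected and any effect on the pain endpoint cannot be computed from the documents.

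**What to change.** Reconcile the two taper paragraphs of Section 5, the strengths in Section 5.3.1, the administration rule in Section 5.3.3 and Appendix 3, so that every taper step can be dispensed in matching blinded capsules. State the strength of the taper supply in Sections 6.2.5.1 and 6.2.6, and describe the supply used for the switch to placebo at randomisation (Sections 5 and 6.2.5.2). Whether the schedule, the supply or the administration rule changes is for the sponsor and investigator.

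The cost is protocol wording and possibly a change to the supply list. Sample size and analysis are not affected.
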